### 3. Précis:

This protocol examines the neurobiology of fear and anxiety using various approaches. During fear conditioning in which a phasic explicit cue (e.g., a light) is repeatedly associated with an aversive unconditioned stimulus (e.g., a shock), the organism develops fear to the explicit cue as well as to the environmental context in which the experiment took place. Experimental evidence suggests that cued fear and contextual fear model different aspects of anxiety. Studies in patients indicated that contextual fear may model an aspect that is especially relevant to anxiety disorders (Grillon et al., 1994, 1998a,b; 1999). However, the neural basis for the expression of contextual fear has not previously been elucidated in human imaging studies.

One important determinant of contextual fear is predictability: contextual fear increases when a threat (e.g., electric shock) is unpredictable, as opposed to when the threat is predictable. The aim of this study is to compare the neural substrates underlying fear evoked by predictable versus unpredictable shocks. Animal studies have indicated that conditioned responses to predictably cued threat and to less explicit threat are separate processes mediated by distinct brain structures. Psychophysiological data suggest that the proposed procedure can differentiate between these two responses. Hence, we anticipate that this procedure will allow us to compare brain correlates of these responses in humans.

Another objective is to study effects of threat of shock on processing and learning of threat cues in the amygdala, the visual and auditory systems, and motivation/reward systems. This will be investigated by means of event-related magneto-encephalography (MEG) and fMRI measurements using various paradigms.

Finally, a last project will examine how pharmacologic manipulation of gamma-aminobutyric acid (GABA) levels with the benzodiazepine alprazolam affects the relationship between GABA concentration (quantified with magnetic resonance spectroscopy, MRS), visual- and auditory-induced gamma oscillations (measured with MEG), and fMRI BOLD response. This project was completed in 2014.

## 1. Introduction and Background:

### 1.1 Fear versus anxiety: different underlying brain mechanisms?

The Diagnostic and Statistical Manual of Mental Disorders (DSM-IV) identifies several anxiety disorders, suggesting heterogeneity of symptoms and etiology among them. In people suffering from explicit cued fear (e.g., specific phobia), fear is associated with an identifiable stimulus that is thought to predict the occurrence of an aversive event. By contrast, sustained anxiety occurs when people have learned that aversive events are both inevitable and unpredictable, in other words, that harm will come without warning (Kandel, 1983; Barlow 2000; Grillon, 2002). The purpose of the fast and intense fear-response is to mobilize resources to enable appropriate flight/fight action. This response is adaptive in the face of an identifiable threat, on which the action can be based. In contrast, anxiety is a feeling of apprehension that is more akin to worrying. It is more sustained and is not generally associated with a clear event. The physiological symptoms of fear and anxiety are rather similar. Hence, the animal experimental literature has often taken these responses as similar besides their intensity and duration. For ease of design, up to date most human imaging studies have focused on cue-specific fear (e.g., fear conditioning, Labar, 1998; Büchel, 1998). The present protocol aims to dissociate brain mechanisms involved in fear and anxiety responses. The characteristics of fear on the one hand, and anxiety on the other hand, can be modeled by responses that are evoked experimentally by either an explicit cue or a context, respectively. Whereas experimentally evoked responses to specific cues capture aspects of (pathological) fear, responses evoked by experimental contexts are un-signaled and, thus, capture some essential characteristics of chronic anxiety. This protocol seeks to understand the neural basis of these different responses.

We have reported data consistent with the hypothesis that patients with anxiety disorders and high trait anxious subjects are excessively sensitive to contextual fear (Grillon et al. 1994; 1998a; 1998b; 1999). For example, veterans with posttraumatic stress disorder (PTSD) exhibit unconditioned enhanced startle responses in environmental contexts where aversive stimuli are expected, compared to experimental contexts where no such stimuli are expected. Moreover, differences in the means of evocation of the response (specific stimulus only in simple phobia) between anxiety disorders suggest differences in the networks involved. Moreover, sensitivity to pharmacological treatment differs across disorders (benzodiazepines are not really successful in the treatment of simple phobia). Additionally, fear-potentiated startle evoked by a discrete stimulus (such as the discrete cues in the proposed fMRI study) has been shown to be insensitive to benzodiazepine treatment in 4 different experiments across two different laboratories (Baas et al., 2002).

Animal research has provided evidence for differentiation between two defense systems. A fast acting, phasic system associated with fear responds to cued threat. A more sustained system associated with anxiety responds to contextual threats that are not tied to a specific cue (Blanchard et al., 1993; Davis, 1999; Lang et al., 2000). Furthermore, these studies have revealed that whereas cued fear is predominantly modulated by the

amygdala (LeDoux, 2000; Davis, 1992), the amygdala, hippocampus (Kim and Fanselow, 1992; Philips and LeDoux, 1992), and bed nucleus of the stria terminalis (BNST, Walker and Davis, 1997) may be involved in contextual fear, though the hippocampus may be primarily involved in processing of contextual cues rather than in generating the fear response. These findings suggest that cued fear and contextual fear are separable processes that are mediated by distinct brain structures. Numerous human imaging studies have demonstrated the activation of the amygdala during cue specific fear responses (e.g., Labar et al., 1998; Büchel et al., 1998). In contrast, sustained states of anxiety in healthy humans have not been extensively explored. Therefore, the main objective of this protocol is to examine the brain mechanisms associated with a sustained state of fear or anxiety in humans.

### **1.2. Rationale: Unpredictability, contextual fear, and sustained anxiety**

Explicit cue fear can be readily evoked using threat or classical conditioning. Contextual fear can be observed in experiments that elicit fear as a response to the experimental context (e.g., the cage, the experimental room) in which the experiment was conducted. Contextual fear is partly determined by the predictability of the aversive event (Seligman and Biknik, 1977; Odling-Smee, 1975). Contextual fear increases with increased shock unpredictability (Odling-Smee, 1975). Unpredictability of aversive events may cause any part of the context in which they may occur to be regarded as unsafe. In contrast, when a discrete cue predicts the occurrence of the shocks, the context becomes a safety signal, reducing contextual fear. In this case, the specific cue will evoke the fear response and the context will become inhibitory (Seligman, 1977; Ameli et al, 2001; Grillon, 2002). Studying the neural systems involved in modulation of defense systems during predictable and unpredictable shock is important for understanding the interplay between fear activation and fear inhibition mechanisms. This is highly relevant to understanding clinical anxiety and fear, since generalization of fears to situations that do not justify them is characteristic of most anxiety and trauma-related disorders.

The present set of experiments will enable us to study the processes associated with phasic cue fear, sustained contextual fear, and inhibitory fear mechanisms. We have shown significant behavioral differentiation between contexts that induce high and low contextual fear by modifying shock predictability. In this procedure, subjects are instructed that in one condition a transient visual stimulus predicts possible shock administration (cue fear), while in another condition a similar visual stimulus (e.g., a blue square) is still presented, but is no longer predictive of the shock. Recent data from this procedure using the startle reflex as a measure of fear showed that giving shocks predictably or unpredictably increased contextual fear compared to a control condition (no shock administered). In addition, contextual fear was smaller in the predictable compared to the unpredictable condition. Furthermore, replicating our previous studies, startle was increased during the presence of the discrete cue in the predictable condition (replicating Grillon 1991, 1993, etc, see section C preliminary results). These results indicate that in this experimental design cued fear and sustained anxiety can be assessed separately. In this study we will explore to what extent the brain systems activated by predictable and unpredictable threat are different.

### 1.3. Human brain imaging studies

Brain imaging studies of the fear or anxiety systems in healthy controls have mostly used conditioned responding to explicit cues (as our specific aim 1). Human studies have yielded ample confirmation of the involvement of the amygdala in emotion in general and in fear and anxiety in particular. Patients with lesions of the amygdala and surrounding areas show impaired fear conditioning. (LaBar et al, 1995). Fear-conditioning (Labar et al., 1998; Büchel et al., 1998), emotional face processing (Morris et al., 1998), instructed threat (Phelps et al., 1999), and processing of threat-related words (Isenberg et al., 1999) all involve the amygdala.

Compared to explicit cue fear, few studies have been conducted on contextual fear or anxiety in humans. In one imaging study that explicitly studied contextual fear conditioning (Armony and Dolan, 2001), a behavioral and a psychophysiological measure failed to confirm a differentiation between conditioned responding (CS+ versus CS-) in a safe (CS+ not reinforced) and a conditioned (CS+ reinforced) context. There was an increase in skin conductance responding to both the CS+ and CS- in the reinforced context suggesting a general increase in arousal. The results showed differences in activation of auditory and parietal cortices, but not in areas implicated in anxiety processing such as the limbic system or areas intimately connected with limbic structures. This pattern of findings is consistent with general arousal or attention, rather than with anxiety.

The crucial comparison in the present design will be to compare background activity (i.e., activity in absence of the transient visual cues) in predictable, unpredictable, and neutral conditions. Our preliminary results suggest that structures involved in contextual fear will be more active in the unpredictable compared to the predictable condition, and in the predictable condition compared to the neutral condition. Hypotheses that can be derived from animal literature are that hippocampus, the amygdala, and related subcortical structures (e.g., extended amygdala, such as the BNST) will be involved in contextual fear. In addition, orbitofrontal areas of the prefrontal cortex (PFC), as well as parts of the anterior cingulate gyrus (medial PFC), are activated in states of anxiety (e.g., Benkelfat et al., 1995; Rauch et al., 1997), and have been implicated in the regulation of the limbic system (Simpson et al., 2001; Drevets, 2000; Davidson and Irwin, 1999; Hariri et al., 2000; Garcia et al., 1999). Therefore, areas of the prefrontal cortex may be involved in both the generation of anxiety, as well as its inhibition. We hypothesize that areas involved in generation of sustained anxiety are activated in the unpredictable condition relative to the predictable and neutral conditions. In addition, inhibitory processes may mediate the decreased contextual fear when threat is predictable. Areas involved in inhibition will be activated during the absence of the specific cue in the predictable condition in comparison with the neutral and unpredictable conditions. Several areas of the prefrontal cortex are likely to be involved in either of these processes: the orbital, medial, and dorsolateral PFC, as well as the anterior insula (see Charney and Drevets, 2002, for a review). In sustained anxiety we predict specifically that the anterior insula, the posterior orbital cortex, and the dorsomedial prefrontal cortex will be activated (specific aim 2a).

The anterior insula is activated in several kinds of anxiety-induction tasks, such as threat of shock as a background to a motor learning task (Chua et al., 1999; PET), and as common area of activation symptom provocation in three different anxiety disorders (Rauch et al., 1997; PET). The orbital prefrontal cortex has been associated with the generation of anxiety, as again in the symptom provocation study (right medial orbital cortex; Rauch et al., 1997), and in threat of shock (Chua et al., 1999, left orbitofrontal cortex; Drevets et al., 1994, posterior orbital cortex).

In the medial PFC / ACC several studies indicate activation with the generation of anxiety. Benkelfat et al. (1995) reported that with CCK4-induced anxiety CBF in the left ACC is increased. Chua et al. (1999) reported activation of the left anterior cingulate gyrus with threat of shock as a background to a motor learning task, if state anxiety scores were used as a covariate (PET). On the other hand, Simpson et al. (2001) reported increased blood flow in two areas of the medial inferior prefrontal cortex (subgenual prefrontal cortex and anterior medial prefrontal cortex) while anticipating shock relative to a baseline non-anxious condition, only in those subjects that reported the highest levels of anxiety. In contrast, subjects with lower levels of anxiety actually showed *decreased* activation in these two areas.

These results suggest that activation in the medial prefrontal area can correlate with generated anxiety positively. However, various support for an inverse relationship between mPFC activation and anxiety has been reported. Lesions of the prelimbic cortex in rats, corresponding to the human dorsomedial PFC, lead to increased freezing to a conditioned tone (Morgan & LeDoux, 1995). Also, an inverse relationship between amygdala activation and firing rate of medial prefrontal neurons has been reported (Garcia et al., 1999).

When human subjects anticipate aversive shocks, the dorsomedial anterior cingulate cortex activation is increased with respect to resting or teeth clenching control, but the degree of activation within each condition is inversely correlated with anxiety ratings (Drevets, 1994). This would suggest that this region is activated to *modulate* emotional responses (Drevets, 1999). Indeed, a recent other study showed a similar inverse relationship between activation of a specific region of the right lateral orbital cortex and the amygdala (Hariri et al., 2000). In addition, research on depression has suggested that in that disorder abnormalities in the ventral anterior cingulate regions (subgenual and pregenual anterior cingulate cortex) may result in abnormal modulation of emotional processing in limbic structures (for a review, see Drevets, 2000). The present protocol allows evaluation of inhibitory influences on the limbic structures in the absence of specific cues in the predictable shock condition. We intend to explore the role of (parts of) the medial prefrontal cortex in the inhibition of anxiety. The prediction is that parts of the medial PFC will be activated in the predictable condition (specific aim 2b). Given evidence mentioned above, parts of the dorsomedial / ACC region may (also) be expected to be also activated in a condition that *generates* anxiety. Therefore, to test specific aim 2b we will evaluate the predictable condition with respect to the neutral baseline condition. In both of the predictable and neutral conditions we expect relatively low contextual anxiety, which in the predictable condition may be due to active inhibitory

processes. In addition, we will also explore the differential involvement of medial prefrontal cortex in the predictable and unpredictable conditions against each other.

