#### **1.6. Preliminary Results**

In the proposed experiment we will use a verbal threat and conditioning through experience to manipulate contextual fear. The procedure was piloted using psychophysiological measures in 15 healthy subjects. The procedure consists of 3

conditions, neutral (N), predictable shocks (P), and unpredictable shocks (U), each lasting 2 minutes. Subjects were informed of the current condition by means of a computer monitor that displayed the following information: “no shock” during the neutral condition, and “shock only during cue” during the predictable and “shock at any time” during the unpredictable shock conditions. During each condition a visual cue (a colored geometric shape) was presented twice, with 8 s duration. As instructed, these cues were relevant only during the predictable condition. In this condition, the cue signaled the possibility of receiving a shock. In the unpredictable condition, shock could be given at any time and in the neutral condition no shock could be administered. Acoustic startle stimuli were delivered in the presence and in the absence of the cues. Figure 1 presents the results, which show that startle was potentiated both by the explicit threat cue and by the threatening context. Indeed, 1) startle was significantly potentiated by the cue only in the predictable shock condition (FPS to specific cue) and 2) there was a significant linear increase in baseline startle in the absence of cues from the N to the P to the U condition (FPS to context). Additional pair-wise comparisons showed significant differences in no-cue startle magnitudes between the N and P conditions and between the P and U conditions. The finding that P elicited contextual fear, compared to N is consistent with our previous studies (Grillon et al., 1993). The finding that U resulted in more contextual fear than P is consistent with both the safety signal hypothesis (19) and conditioning theories (20), which predict that the presence of a signal for shock reduces fear to the context.

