## **2. Study Objectives:**

The overall objective of this protocol is to investigate the brain correlates of responses to predictable and unpredictable shocks. Several contrasts derived from the design will allow this investigation.

- A) Explicit cue fear will be evoked by the presentation of a specific cue that is associated with an electric shock. In order to study explicit cue fear we will examine the BOLD response to the presentation of cues that predict a shock (fMRI study). We predict that the amygdala will be activated in this comparison, along with several cortical areas that are involved in explicit cue fear, in particular the anterior insula (Phelps et al., 2001) and the anterior cingulate (Büchel et al., 1998). In addition, sensory processing of auditory and visual stimuli that predict threat will be facilitated (MEG/fMRI study). This will be reflected in the augmentation of the activation evoked in sensory areas and the amygdala to those stimuli relative to non-threatening stimuli.
- B) In contrast, sustained contextual fear or anxiety will be elicited by unpredictable aversive events. To measure this background state, we will compare the BOLD responses during conditions in which subjects anticipate shocks being delivered predictably and unpredictably to conditions where no shocks are anticipated. In all hypotheses concerning the background state of anxiety, BOLD responding during the absence of the explicit cues will be utilized.
  - 1) In order to evaluate activations associated with the sustained anxiety state in the unpredictable condition, the contrasts of unpredictable shock versus neutral and versus predictable shock will be used. Regions that are hypothesized to be activated are the amygdala, and the anterior insula, as well as posterior orbital cortex and dorsomedial prefrontal cortical areas.
  - 2) A second hypothesis with regard to the sustained state of anxiety is that in the condition where shock is predictable, this sustained state is inhibited in comparison to the condition in which the shock is unpredictable. To evaluate this hypothesis, the contrasts predictable shock versus neutral and versus unpredictable shock will be used. We predict that in the predictable shock condition, areas of the lateral orbital cortex, and ventral anterior cingulate cortex are activated in comparison with the unpredictable shock condition, as well as the neutral condition.

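### The contrast named for aim 2b, predictable versus neutral, cannot by itself separate inhibition of anxiety from anxiety, and the sections disagree on whether predictable versus unpredictable must also hold

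*Combined protocol and SAP*

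**What the plan says.** The conditions are neutral (N), predictable shock (P) and unpredictable shock (U). Aim 2b concerns background BOLD, measured while no cue is present.

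- **Section 1.3, final paragraph.** The named test is: "Therefore, to test specific aim 2b we will evaluate the predictable condition with respect to the neutral baseline condition". The reason given is that "parts of the dorsomedial / ACC region may (also) be expected to be also activated in a condition that *generates* anxiety". The premise is: "In both of the predictable and neutral conditions we expect relatively low contextual anxiety". The other contrast is secondary: "we will also explore the differential involvement of medial prefrontal cortex in the predictable and unpredictable conditions against each other".
- **Section 1.3, paragraph on the crucial comparison.** Contextual-fear structures are expected to be more active in U than in P, "and in the predictable condition compared to the neutral condition". The same paragraph expects inhibitory areas to be more active in P than in both N and U.
- **Section 1.2.** Earlier startle data are described as showing more contextual fear under either kind of shock than with no shock, and less under P than under U.
- **Section 1.6.** "The procedure was piloted using psychophysiological measures in 15 healthy subjects". No-cue startle rose linearly from N to P to U. Pairwise tests gave "significant differences in no-cue startle magnitudes between the N and P conditions" and also between P and U. The authors conclude that P elicited contextual fear.
- **Section 2, objective B2.** For inhibition, "the contrasts predictable shock versus neutral and versus unpredictable shock will be used", with activation predicted in P relative to U as well as to N.
- **Section 10.a.** Context is modelled as a three-level blocked factor. Tests in 8 regions (4 per hemisphere) are corrected for type I error by an unnamed method. No rule says which contrast, or combination, decides aim 2b.

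**The concern.** P versus N was chosen to keep generated anxiety out of the inhibition test. That works only if P and N differ little in contextual anxiety. The protocol's own pilot, its summary of earlier data and its own expectation for fear structures all put P above N. P>N is then the predicted sign under both accounts, so a significant result does not distinguish them. The contrast that can do so is P versus U, where a pure anxiety region should be lower in P and an inhibitory region higher. The paragraph that names the test gives that contrast exploratory status.

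At stake is the inference. An analyst who follows Section 1.3 literally could report a region that tracks anxiety as evidence of inhibition and still comply with the protocol.

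**Working it through.** The documents give no sample size, power or BOLD effect for aim 2b, so there is no plan figure to reproduce. The check is first one of logic, then an illustration of size.

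**1. Predicted signs for no-cue BOLD**

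| Region type | P versus N | P versus U |
|---|---|---|
| Generates anxiety (pilot ordering N<P<U) | P>N | P<U |
| Inhibits anxiety (Section 1.3 and Section 2 B2) | P>N | P>U |
| Inhibits in P and generates in U | P>N | unclear, possibly no difference |

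Only the second column separates the first two rows.

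**2. What the pilot implies.** With n=15 and an assumed two-sided .05 level, a significant P versus N difference needs an observed dz of at least 2.145/√15 = 0.55. The startle difference between P and N was therefore not trivial. It is startle, not BOLD, and does not show which regions carry it.

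**3. How often an anxiety region passes P>N.** Inputs:
- n=15 and 20, the usable data per experiment, and n=30, the approximate recruitment (Section 4.v).
- Two-sided paired t tests.
- Equal N-to-P and P-to-U steps of dz 0.5. This is an assumption. It is the medium paired effect that Section 10.c uses for the MEG incentive task and the avoidance task, not a value given for this aim.

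Probability = 1 − F(t_crit; n−1, dz√n), where F is the noncentral t distribution function. Bonferroni over 8 regions is also an assumption, giving .05/8 = .00625.

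| n | dz√n | t_crit at .05 | P>N significant | t_crit at .00625 | P>N significant |
|---|---|---|---|---|---|
| 15 | 1.936 | 2.145 | .44 | 3.214 | .15 |
| 20 | 2.236 | 2.093 | .56 | 3.074 | .24 |
| 30 | 2.739 | 2.045 | .75 | 2.949 | .43 |

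At alpha .05 and n=15, the first probability runs from .19 at dz 0.3 to .99 at dz 1.2.

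**4. Requiring P>N and P>U.** This was simulated with independent, equal noise in the three conditions, scaled so that each pairwise difference has SD 1. At alpha .05, over n=15 to 30 and dz 0.3 to 1.2, the anxiety region passes both tests in under .001 of runs.

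**5. Price for genuinely inhibitory regions, n=20 (same noise model)**

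| P above N (dz) | U above N (dz) | P>N alone, .05 | Both, .05 | P>N alone, .00625 | Both, .00625 |
|---|---|---|---|---|---|
| 0.5 | 0 | .56 | .40 | .24 | .11 |
| 0.8 | 0 | .92 | .87 | .69 | .53 |
| 0.8 | 0.4 | .92 | .39 | .69 | .12 |
| 0.8 | 0.8 | .92 | .02 | .69 | .003 |

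The last two rows are the mixed-role case.

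**The case against.** A reader might infer that aim 2b is tested only as P versus N, so that an anxiety-generating region would be read as inhibitory. The documents do not support that. Section 2 B2 commits to both contrasts and predicts P above U as well as above N, and an earlier paragraph of Section 1.3 says the same. Under those statements an N<P<U region fails the prediction. What stands is narrower: one paragraph ranks P versus U as exploratory, two other places do not, and Section 10 does not settle it. Misreading is possible, not built in.

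A reader might also infer that the pilot refutes the premise. The premise is of low anxiety in relative terms, not equal anxiety, and the pilot did find P below U. The premise is incomplete rather than false: it leaves out the P-over-N difference that matters for this contrast.

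Section 2 also names different regions: lateral orbital and ventral anterior cingulate cortex for inhibition, and amygdala, anterior insula, posterior orbital and dorsomedial prefrontal cortex for generation. This protects only in part. Section 1.3 frames aim 2b around parts of the medial prefrontal cortex, and Section 10.a has one undivided anterior cingulate region and no lateral orbital region.

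The strongest counter-argument is that N was chosen for a reason. A region that inhibits in P may generate anxiety in U, and P versus U would then hide it. That stands, and it is a real cost of requiring both contrasts.

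**Conclusion.** The concern holds in this form: the P versus N test named in Section 1.3 cannot on its own support a conclusion of inhibition, and the protocol is inconsistent about whether P versus U must also hold. Under equal steps of dz 0.5, an anxiety-generating region would pass P>N with probability .44 to .75 at n=15 to 30 without correction, or about .15 to .43 under Bonferroni, and would pass both contrasts in under .001 of runs. These figures rest on an assumed effect size, equal steps, an independent-noise model and, for the lower range, an assumed correction method. The sign argument does not depend on them, but it does assume that BOLD in an anxiety region follows the ordering seen in startle.

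This should be fixed before analysis. It is not fatal: all three conditions are collected and modelled, aim 2b is one sub-hypothesis, and the protocol already states the two-contrast prediction elsewhere.

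**What to change.** Reconcile the aim 2b paragraph of Section 1.3, and Section 10.a, with the two-contrast prediction in Section 1.3 and Section 2 B2:

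1. State that a region is reported as supporting inhibition only if no-cue BOLD is higher in P than in N and higher in P than in U. Test each contrast at the region-corrected level. Because both must be significant, no further split of alpha is needed within a region.
2. State that P>N without P>U is reported as threat-related activation that does not distinguish inhibition from generated anxiety.
3. Correct the premise in Section 1.3 so that it acknowledges the pilot finding of more contextual fear in P than in N.
4. Name the multiplicity method for the 8 regions in Section 10.a, since the operating characteristics depend on it.

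The change needs no new data, participants or procedures. It does cost power for a true inhibitory region: at n=20 and alpha .05, from .56 to about .40 at dz 0.5 and from .92 to .87 at dz 0.8. Under Bonferroni these become .24 to .11 and .69 to .53. Regions that inhibit in P and also generate anxiety in U will usually fail the joint rule. The protocol should say that they are left as indeterminate, not counted as evidence against inhibition.
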